#### Analysis Populations

## Intention-to-treat population

All patients who meet eligibility criteria and receive at least one dose of the study drug will be included in the analysis of the primary and secondary endpoints, even if there are subsequent protocol deviations.

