# **STUDY DESIGN**

# General Design

This is a multi-center, two-arm, open-label, phase 1b/2 study evaluating the anti-tumor effect of either Nivolumab alone or Nivolumab plus BMS-986253 with androgen deprivation therapy using Degarelix in men with hormone-sensitive prostate cancer and a rising PSA. Patients will be recruited from outpatient clinics at participating sites and randomized to either Nivolumab alone (Arm A) or Nivolumab plus BMS-986253 (Arm B).

**Study Interventions:** Eligible patients in Arm A will receive Nivolumab every 4 weeks for 2 doses and then Nivolumab + Degarelix every 4 weeks x 4 doses. Eligible patients in Arm B will receive Nivolumab every 4 weeks x2 doses + BMS-986253 every 2 weeks x 4 doses and then

Nivolumab every 4 weeks x 4 doses + BMS-986253 every 2 weeks x 8 doses + Degarelix every 4 weeks x 4 doses.

Schedule of Evaluations: During treatment patients will have safety assessments including routine bloodwork and physical examinations at each visit. (See Section 12 for detailed study evaluations and the study schedule). Safety evaluations will also occur until 100 days after the last treatment doses.

The primary endpoint will be evaluated by assessing the PSA 10 months after start of therapy. PSA and serum testosterone will be checked monthly during treatment (+/- 3 days), the end of treatment visit (+/- 1 week), every 2 months (+/- 1 week) or until progression of disease during year 1 of follow up and every 3 months (+/- 1 month) or until progression of disease during year 2 of follow up. Sera, whole blood and CBC with differential will be collected for immunoassays at initiation of immunotherapy, at initiation of degarelix, end of treatment visit and 10, 14 and 18 month (+/- 1 week). Patients will also have CT or MRI scans (chest, abdomen and pelvis) and bone scan at screening, end of treatment and 10 months after start of therapy. Toxicity evaluation will utilize CTCAE v5.0 criteria.

**Duration of Treatment:** Subjects will receive treatment for a total of 6 months or intolerable toxicity or side effects.

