#### Study Endpoints

We will use one-sided binomial tests to compare the post-therapy PSA recurrence rate in each arm with the historical recurrence rate of 50%. To compare the secondary outcomes between the two arms, Kaplan-Meier estimators and log-rank tests will be used to compare time-to-event variables (e.g., time to PSA recurrence, time to recovery of testosterone, and time to next anti-cancer treatment); Chi-squared tests will be used to compare incidence rates (e.g., incidence of metastases); t-tests will be used to compare continuous measurements (e.g., changes immune cell density and proximity). We will set the nominal significance level at 5%. Only patients undergoing randomization to the treatment arms will be used for comparison between the treatment arms.

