## Safety population

All patients enrolled in the study will be included in the safety analysis population and considered evaluable for toxicity from the time of their first dose of the study drug(s). Patients never receiving any of the study drugs will not be included in this analysis. Demographic and baseline characteristics for the safety population will be summarized by number and percent for categorical data and by descriptive statistics for continuous data.

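### The set labelled intention-to-treat holds only eligible, dosed men, so the between-arm secondary comparisons may omit some randomised men, and no defined population keeps them

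*Combined protocol and SAP*

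**What the plan says.** Under Analysis Populations, the section headed "Intention-to-treat population" states: "All patients who meet eligibility criteria and receive at least one dose of the study drug will be included in the analysis". The sentence continues: "of the primary and secondary endpoints, even if there are subsequent protocol deviations". One set therefore governs every primary and secondary endpoint. Entry to it needs two things, meeting the eligibility criteria and receiving a dose.

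General Design describes a "multi-center, two-arm, open-label, phase 1b/2 study" in which men are randomised to Arm A or Arm B. Study Endpoints sets out two kinds of analysis:

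- The primary analysis is a one-sided binomial test of each arm against a historical 50%.
- The secondary analyses compare the arms: "To compare the secondary outcomes between the two arms, Kaplan-Meier estimators and log-rank tests will be used to compare time-to-event variables". Chi-squared tests are planned for incidence rates and t-tests for continuous measures, all at a nominal 5%.

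Study Endpoints adds: "Only patients undergoing randomization to the treatment arms will be used for comparison between the treatment arms". The Safety population section says of undosed men: "Patients never receiving any of the study drugs will not be included in this analysis".

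**The concern.** Intention-to-treat normally means everyone randomised, analysed in the arm assigned. The set defined here is an eligible-and-treated set. Its two entry conditions can be settled after the arm is known, because the trial is open-label. A man may decline before his first dose once he learns his assignment, and the wording would also allow a man to be removed as ineligible after randomisation.

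The between-arm tests are the only inferences in the plan that rest on randomisation. If the men left out differ between arms in number or prognosis, those tests compare groups that randomisation no longer balances. A report would still call the result intention-to-treat. Even if nobody is excluded, the label is wrong and would be carried into publication.

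**Working it through.** **1. The plan's own figure.** Inputs from Study Design and Sample Size: null rate 0.50, alternative 0.25, type I error 0.05, type II error 0.20, 23 evaluable men per arm, 20% dropout, 30 enrolled per arm. Study Endpoints makes the test one-sided.

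- Exact binomial with n = 23, rejecting at 7 or fewer recurrences: P(X ≤ 7 | 23, 0.50) = 0.0466 and P(X ≤ 7 | 23, 0.25) = 0.804.
- Dropout: 23 / (1 − 0.20) = 28.75, so 29, against 30 planned.

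The sample size reproduces and is not in dispute. The point concerns who is analysed.

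**2. Where each randomised man goes.**

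| Randomised man | Set labelled intention-to-treat | Safety population |
|---|---|---|
| Eligible, dosed | in | in |
| Eligible, never dosed | out | out |
| Found ineligible, dosed | out | in |
| Found ineligible, never dosed | out | out |

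The Study Endpoints sentence on randomised patients does not change this table. It limits the comparison to randomised men; it does not say that all of them are included. The allowance for later protocol deviations protects only men already in the set.

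**3. Size between arms (illustration).** Assumptions, none from the documents except the 30 per arm: a true recurrence rate of 40% in both arms, so 12 of 30 in each; m men dropped from one arm only; their outcomes known. The recurrence proportion stands in for the planned time-to-recurrence comparison.

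- All m recurred: shift = (12 − m)/(30 − m) − 0.40
- None recurred: shift = 12/(30 − m) − 0.40

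| m | All recurred | None recurred |
|---|---|---|
| 1 | 11/29 = 0.379, −2.1 points | 12/29 = 0.414, +1.4 points |
| 2 | 10/28 = 0.357, −4.3 points | 12/28 = 0.429, +2.9 points |
| 3 | 9/27 = 0.333, −6.7 points | 12/27 = 0.444, +4.4 points |

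Varying the common rate from 30% to 50%, one man moves the difference by 1.7 to 2.4 points if he recurred and by 1.0 to 1.7 points the other way if he did not. For scale, the standard error of the difference at 40% is √(2 × 0.4 × 0.6 / 30) = 0.126, or 12.6 points. The largest shift in the table is about half of that (6.7/12.6 = 0.53).

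**4. The one-sample tests.** With 30 men assessed, the arm rejects at 10 or fewer recurrences (P(X ≤ 10 | 30, 0.50) = 0.049; for 11 it is 0.100). Exclusions can move a borderline result either way:

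- 11/30 (p = 0.100) becomes 9/28 (p = 0.044) if two recurrent men are removed.
- 10/30 (p = 0.049) becomes 10/28 (p = 0.092) if two non-recurrent men are removed.

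The first case starts one event above the cut-off and needs both excluded men to be recurrent. If two of the 30 were excluded regardless of outcome, that chance is (11 × 10)/(30 × 29) = 0.126.

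**The case against.** Much can be said for the plan.

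- **The primary analysis is one-sample.** Randomisation does not protect a comparison with a historical 50%, and a dosed set is a usual choice there. This stands, and the fix keeps a dosed set for it.
- **A reader might infer that two exclusions overturn an arm's primary result.** The documents do not support that as an expectation. They give no number of ineligible or undosed men, and step 4 shows a worst case that can run in either direction.
- **A reader might infer that Arm B's 12 infusion days, against 6 in Arm A, or a poor early course, would remove men from the set.** Neither can do so through the dosing condition. After one dose an eligible man stays in despite later deviations. The heavier schedule matters only if it leads a man to decline before starting, and both arms begin with active nivolumab, so few may do so.
- **A reader might infer that eligibility is re-judged after randomisation.** The wording permits this but does not state it. General Design speaks of eligible patients receiving treatment, which fits eligibility settled beforehand. The eligibility and registration sections are not in the text available for review, so it cannot be said that the plan is silent on who judges eligibility and when.
- **The stakes are limited.** The between-arm tests are secondary, at a nominal level, and the stated power does not cover them. Immune measures come from a biopsy subset of at least 10 per arm, where an all-randomised set is not attainable. Relapse-free survival is defined after testosterone recovery, so widening the population would not by itself make that a fully randomised comparison.

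These arguments reduce the importance of the point. None of them makes the label correct or supplies a population that keeps every randomised man.

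**Conclusion.** The point holds as one of definition and labelling, with a possible bias in the between-arm secondary comparisons. The set called intention-to-treat is an eligible-and-dosed set, and undosed men are in no defined population.

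The size is unknown. Under the assumptions in step 3, one to three one-sided exclusions shift the difference by about 2 to 7 points if all recurred, or 1 to 4 points the other way if none did. If few men are excluded, or exclusions are alike in both arms, the effect is small. The sample size and the primary one-sample design are unaffected. This should be corrected before analysis, but it does not undermine the trial.

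**What to change.** In Analysis Populations:

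1. Define intention-to-treat as all randomised men, analysed in the arm assigned. Use it for between-arm comparisons of clinical secondary outcomes. Immune measures from the biopsy subset stay on men with samples.
2. For these comparisons, measure time-to-event outcomes from randomisation. The primary endpoint runs from the start of therapy, and an undosed man has no such date.
3. Rename the dosed set *modified ITT (all dosed)*, drop the eligibility condition from it, and use it for the one-sample tests against 50%.
4. Keep the present eligible-and-dosed set as a sensitivity analysis.
5. Report the men excluded from each set by arm, with reasons.

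The cost is more than wording, but small: a time origin for the between-arm comparisons, a little extra follow-up of undosed men, and slight dilution of any treatment difference. Neither enrolment nor treatment changes.

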## Safety population

All patients enrolled in the study will be included in the safety analysis population and considered evaluable for toxicity from the time of their first dose of the study drug(s). Patients never receiving any of the study drugs will not be included in this analysis. Demographic and baseline characteristics for the safety population will be summarized by number and percent for categorical data and by descriptive statistics for continuous data.

